3.3.5. Blood pressure, urinalysis and biochemical markers

Blood pressure, urinalysis, and biochemical indicators of serum glucose, cholesterol, triglycerides, and creatinine were measured before the start of the trial and after the four weeks of consumption of the beverage were completed, to compare these parameters before and after treatment. The measurements and blood samples were taken by trained and experienced personnel. Blood pressure was measured using a noninvasive technique using the Korotkoff auscultation method.

Blood samples were obtained by puncture in the antecubital region of the participants' non-dominant arm, using sterile, disposable materials. Blood was placed in anticoagulant-free tubes for clinical chemistry, extracting 6 ml of blood. These tubes were kept refrigerated until the determinations were performed in the Biomarker Measurement Laboratory of the Biotic Product Development Center by personnel from the Department of Nutrition and Functional Foods, who are trained and experienced in sample collection and processing. Blood chemistry was measured using the Spinlab series 5-5312 semi-automated turbidimetry equipment for clinical chemistry.

The biological materials were used only for the aforementioned tests and were kept refrigerated until their disposal as Biologically Infectious Hazardous Waste (BIHW) in accordance with Mexican Official Standard NOM-087-SEMARNAT-SSA1-2002. The

results of the biochemical indicators were reported in writing to the participants, who received free medical and nutritional guidance, if necessary.

The general urine test was performed by the Jacobo Curiel external clinical analysis laboratory in Cuernavaca, Morelos. Participants submitted their samples to the "MEDOMAI" clinic on the indicated date, and the samples were then transferred to the external laboratory.

The researchers of this protocol declare that there is no conflict of interest and that the objective is to generate knowledge that allows us to evaluate the effect of a beverage with *H. sabdariffa*, which can be used in the prevention and/or treatment of hypertensive disorders associated with pregnancy, as well as to determine its degree of gastrointestinal acceptability and tolerability.

4. SCHEDULE OF ACTIVITIES

Activity	2024				
	March	April	May	June	July
Information meeting with potential participants	X	X			
Interviews to verify inclusion criteria		X			
Participants selection		X			
Measurement of blood pressure and biochemical indicators before the test.		X			
Beverage acceptability and tolerability test			X		
Measurement of blood pressure and biochemical indicators after the test			X		
Analysis of results			X	X	
Preparation and submission of the report to the Research Ethics Committee					X

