2.2. Specific objectives

- To evaluate the acceptability of the beverage by sensory analysis in a 4-week trial with a 7-point hedonic scale.
- Determine the tolerability of the beverage by the presence of gastrointestinal symptoms.
- Evaluate biochemical indicators, blood pressure and general urine test before and after the beverage consumption trial.

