3. MATERIAL AND METHODS

A 4-week phase I pilot trial was conducted in 10 women in their second trimester of pregnancy, who consumed a daily dose of *H. sabdariffa* beverage. Acceptability and tolerability were assessed. Blood pressure, urinalysis, and blood biomarkers of glucose, cholesterol, triglycerides, and creatinine were also measured.

Figure 1 presents the experimental diagram of the beverage acceptability and tolerability test.

[figure not shown]

Figure 1. Experimental diagram of the acceptability and tolerability test of a beverage with *Hibiscus sabdariffa* L.

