3.1. Ethical considerations

This research project complies with the International Ethical Guidelines for Research Related to Human Health, developed by the Council for International Organizations of Medical Sciences (CIOMS) in collaboration with the WHO.

All participants in this trial received dignified treatment and were not discriminated against under any circumstances based on their ethnic or national origin, social or economic status, religion, opinions, or marital status, in accordance with the Federal Law to Prevent and Eliminate Discrimination. Participants were never recruited against their will, nor did they suffer any form of disapproval or retaliation if they decided not to participate or withdrew from the study. It was emphasized that participation was completely voluntary and that they could refuse to participate or withdraw from the research at any time if they so desired.

The results obtained were used solely by the research team. The privacy of the participants, as well as the confidentiality of their personal information, was protected. All collected samples were identified by the participant's initials and a consecutive number, and only the researchers had access to their personal information. This information was kept safe with their file and will not be disclosed or published at any time. The results may be published for scientific purposes, but personal and identifying data of the participants will not be disclosed at any time. The results obtained were analyzed using Past software through pairwise analysis to determine statistical differences between the indicators measured before and after treatment with a significance level of $P < 0.05$. Descriptive statistics with means, standard deviations, and percentages were also applied to characterize the group.

The researchers of this protocol declare that there is no conflict of interest and that the objective is to generate knowledge that allows us to evaluate the effect of a beverage with *H. sabdariffa*, which can be used in the prevention and/or treatment of hypertensive disorders associated with pregnancy, as well as to determine its degree of acceptability and tolerability.

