3.3.2. Participants selection

Because this was a phase 1 pilot study, where participants were self-controlled, with marker measurements taken before starting to consume the beverage and at the end of the 4-week treatment period, the sample size was based on convenience. All women who met the inclusion criteria and did not meet the exclusion criteria were invited to participate. At least ten pregnant women were recruited through the consultation of PhD. [name], a specialist in obstetrics and gynecology and maternal-fetal medicine at the "MEDOMAI" Comprehensive Health Services Clinic located in Cuernavaca, Morelos, México.

Participants were selected according to the following criteria:

Inclusion criteria

- Pregnant women aged 18 to 35
- Those in their second trimester of pregnancy (14 – 28 gestation weeks)
- Blood pressure <140/90 mmHg

Exclusion criteria

- Multiple or high-risk pregnancy
- Having suffered from a hypertensive disorder in previous pregnancies

- Having chronic non-communicable diseases such as diabetes mellitus, cardiovascular disease, cancer, and chronic kidney disease
- Body Mass Index $\geq 32 \text{ kg/m}^2$

Elimination criteria

- Develop any pregnancy complications that prevent you from consuming the beverage and/or attending the measurements
- Deciding of your own volition to withdraw from the study

The patient records were reviewed to select patients who met the criteria for pregnancy weeks and age. They were contacted by telephone, where their medical history was taken to confirm that they met the remaining criteria. The procedures to be performed and how to prepare the beverage were explained in detail. In this conversation, the candidates were asked about their interest in participating and the date they should arrive to sign the informed consent form, receive the powdered doses to prepare the beverage along with its preparation instructions, and perform blood pressure measurements, biochemical indicators, and provide a urine sample.

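### Does the missing limit on time from baseline to first dose spoil the before-after comparison?

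*Protocol*

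**What the plan says.** Section 2.2 makes the before-after comparison a specific objective: "Evaluate biochemical indicators, blood pressure and general urine test before and after the beverage consumption trial". Section 3 describes a four-week trial in women "who consumed a daily dose of" the beverage.

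Two places give the order of the measurements. Section 3.3.2 has "marker measurements taken before starting to consume the beverage and at the end of the 4-week treatment period". Section 3.3.5 puts the first set before the trial starts and the second "after the four weeks of consumption of the beverage were completed".

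Section 3.3.2 also describes the first visit. On one date the woman was to sign consent, "receive the powdered doses to prepare the beverage along with its preparation instructions, and perform blood pressure measurements", and have the biochemical indicators and urine sample taken.

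Section 3.1 says the data were compared by "pairwise analysis to determine statistical differences between the indicators measured before and after treatment", at a significance level of P < 0.05.

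The calendar in section 4 has one column per month. "Measurement of blood pressure and biochemical indicators before the test" is marked in April only. The beverage test and "Measurement of blood pressure and biochemical indicators after the test" are both marked in May only.

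**The concern.** Each woman is her own control and there is no parallel group, so anything that changes with time enters the before-after difference. Blood pressure and blood chemistry may drift as pregnancy advances. If a woman was measured in April but did not start drinking until May, the untreated weeks count in her difference as though they belonged to the beverage. If baseline dates were spread over April, the untreated time would also differ from woman to woman, and with about ten women a few long gaps could matter.

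The text sets the order of events but no limit in days. Dispensing and baseline share one date, yet nothing says drinking began that day. Starting on an April dispensing date would put consumption in a month the calendar does not mark. Waiting until May, as the calendar has it, creates a gap. At stake are the blood pressure, urine and biochemical comparisons. The weekly acceptability and tolerability forms do not use the baseline and are unaffected.

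**Working it through.** The protocol states no interval between baseline and first dose, so there is no figure to reproduce. The check is which dates the text permits.

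**Inputs**
- Baseline: 1 to 30 April 2024 (section 4).
- Consumption: 4 weeks × 7 daily doses = 28 doses (section 3), all in May 2024 if section 4 is read literally.
- After-measurement: on or after the last dose, by 31 May (sections 3.3.2, 3.3.5 and 4).

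**First dose.** The last dose falls 27 days after the first. A start on 1 May ends on 28 May and a start on 4 May ends on 31 May. A later start does not fit, so the first dose is on 1 to 4 May.

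**Gap from baseline to first dose.** Shortest: 30 April to 1 May = 1 day. Longest: 1 April to 4 May = 33 days.

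**Interval from baseline to after-measurement (28 to 31 May)**

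| Baseline | Gap to first dose | Before-after interval |
|---|---|---|
| 30 April | 1–4 days | 28–31 days |
| 15 April (assumed, for illustration) | 16–19 days | 43–46 days |
| 1 April (outer bound) | 30–33 days | 57–60 days |

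The outer bound is 60/28 = 2.1 times the exposure. If the after-measurement must come at least a day after the last dose, the first dose is on 1 to 3 May and the shortest interval is 29 days; the longest is still 60.

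**What the table shows.** The first row satisfies every section, so sections 3.3.2, 3.3.5 and 4 are compatible. Its interval exceeds the exposure by 0 to 3 days. The other rows need a baseline date that the protocol does not give. The 1 April row is also unlikely on the calendar's own terms, because the eligibility interviews and the selection of participants are marked in April too and would normally come before baseline.

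**How much the calendar can bear.** It has one mark per activity per month and also covers information meetings and the report to the ethics committee. It gives no dosing dates. A May mark is consistent with every dose falling in May, and also with most of the test falling there after a start in the last days of April. Day-level gaps drawn from it are limits on what is possible. They do not estimate what happened.

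**Variation between women.** Nothing visible shows that baseline dates were spread out. For about ten women at one clinic, one session or a few close ones would fit the text equally well.

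**Size of any bias.** This would need the change per week of pregnancy in each marker, times the gap in weeks. The protocol gives neither, so the bias cannot be computed.

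**The case for a change.** The best case for acting is that visit timing belongs in the protocol and no later analysis can shorten a gap that has already occurred. Four weeks of advancing pregnancy come with the design, whereas an untreated lead-in is avoidable. The introduction says the pilot is meant to settle logistics for a later randomized trial, and baseline timing is part of those logistics. Stating a window would cost almost nothing.

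Much of this is right. The visible text gives no limit in days, the arithmetic is sound, and a baseline close to the first dose is good practice for the next trial. But it shows something left unwritten, not something stated wrongly. Section 3.3.2 already ties the baseline to the handing-out of powder with preparation instructions. The ordinary reading is that drinking began soon afterwards, and no section describes a waiting period. Figure 1 is an obvious place for the timing and cannot be seen, so its absence from the rest of the text does not show that the plan lacks it. The protocol is written in the past tense, so a new window could not alter measurements already taken.

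**Conclusion.** The concern does not call for a change. The sections can all be followed together with a before-after interval of 28 to 31 days, so following the plan as written need not give a worse result. Intervals of up to 60 days are possible only under a literal day-by-day reading of a monthly calendar, and neither a delay nor a difference between women is shown.

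The remaining gap is one that analysts fill sensibly. Measurement dates and gestational ages allow each woman's actual interval to be described when results are reported. Any lead-in would add an amount of unknown size, possibly close to zero, to a larger limitation the design already carries: four weeks of advancing pregnancy without a control group. That limitation alone rules out crediting the whole change to the beverage, whatever the gap was.

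This conclusion assumes that consumption began soon after the dispensing visit, as section 3.3.2 suggests, and that Figure 1 says nothing to the contrary. Evidence of gaps of several weeks would affect how the blood pressure, urine and biochemical results are read. It would not touch acceptability or tolerability.

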ANNEX

100 Aniversario del CECyT "Gonzalo Vázquez Vela"
60 Aniversario del Centro Cultural "Jaime Torres Bodet"
50 Aniversario de la ESIME Unidad Culhuacán,
ESIA Unidad Tecamachalco y de la Escuela Superior de Turismo
40 Aniversario del CIIEMAD, CEPROBI y del CITEDI

1. From the protocol:

- Align the title with the study **objective**. It should match the statements in the three reviewed documents (**protocol**, **consent form**, and **study summary**). Ensure that it addresses the study **variables**, both dependent and independent. It was suggested to simplify it with the following: "**Evaluation of blood pressure, tolerability, and acceptability of Hibiscus sabdariffa L. in pregnant women.**"
- Clarify the research design and its **scope**, based on the maturity of the project, recognizing, if applicable, that before implementing the study with the appropriate design and sample, an **evaluation of the instruments, resources to be employed, and the feasibility of the designed logistics** is intended.
- With the current design, and in order to expand the sample size, it is suggested, if appropriate for the research group, that a **control group with regular consumption of Jamaican** be included. This would accurately demonstrate the **comparability or efficacy of the product**.
- Add available quality **information of the product** (technical sheet): average anthocyanin content (ds), variety to be used, origin of the material and the minimum physical-chemical specifications for its adequate characterization..
- It is recommended to include the training of human resources in postgraduate studies in the **contributions section of the study**.
- In any case, any **changes or modifications to the original protocol** must be noted and notified to the committee.

2. Informed consent.

- Standardize information in the **protocol and consent forms** regarding benefits for participants (nutritional, medical, or both) and duration (whether it will be only during the study or until the end of the pregnancy).

3. Summary of previous studies.

- A systematic review and clinical trial strategy should be undertaken to justify and clarify the sample size and selection with greater evidence. The review should consider the type of subjects, recruitment strategy and inclusion, exclusion, and elimination criteria, the number and size of groups, the method and quantity of the product being evaluated, and the effect size and precision. It is suggested that searches be conducted in databases such as the Cochrane Library and PubMed.
